TITLE: Use of High Flow Nasal Cannula during Sedation of Morbidly Obese Patients in the Endoscopy Suite

Authors:

[name] MD/ PhD

[name] MD

BACKGROUND

Obesity defined as a body mass index (BMI) of $> 30 \text{ kg/m}^2$ has been identified as an independent predictor of sedation-related complications in patients undergoing sedation for gastro endoscopic procedures^{1,2,3}. A recent survey estimated that in 2011-2012 34.9% of adults in the United States were obese (BMI $> 30 \text{ kg/m}^2$) and 6.4% were extremely obese (BMI $> 40 \text{ kg/m}^2$)¹. Several physiologic changes occur, as a patient's BMI increases from the normal range to the extremely obese range. Respiratory physiology in morbidly obese patients is altered; specifically, the additional weight of the chest causes a decrease in chest wall motion and lung compliance. The decrease in compliance increases the work of breathing and causes the development of ventilation to perfusion mismatching⁴.

In addition to physiologic changes, increasing obesity also causes anatomical changes that affect the respiratory system. The high incidence of obstructive sleep apnea in obese patients can interfere with gas exchange during

endoscopic procedures requiring chemical sedation by causing airway obstruction⁵. The effect positional changes have on oxygen saturation is amplified in obese patients⁶. The physiologic and anatomic changes associated with obesity not only necessitate an increased vigilance when monitoring these patients receiving deep sedation, but also commonly require airway manipulation to ensure proper oxygenation and ventilation.

The delivery of anesthesia used for obese patients for gastrointestinal procedures does not significantly differ from what is used in healthy patients. Patients often receive deep sedation, a state in which patients are not easily arousable, but are responsive to noxious stimuli. Typically sedation during endoscopic procedures is maintained with an intravenous anesthetic such as Propofol; however, the choice of anesthetic used is operator dependent and should be personalized to the patient's medical history⁷. Regardless of the level of sedation, patients undergoing endoscopic procedures are typically provided with supplementary oxygenation via nasal cannula or face mask when a higher concentration of oxygen is required^{8,9}. As a means to maintain ventilation in cases complicated by airway obstruction, physical maneuvers such as a chin lift or jaw thrust may be performed, adjuncts such as oral and nasal airways may be placed, and lastly active positive pressure ventilation may be delivered via bag valve mask (BVM), laryngeal mask airway (LMA), or endotracheal tube (ETT)⁸. The use of

high flow nasal cannula (HFNC) to deliver oxygen to morbidly obese patients is expected to decrease the need for the aforementioned interventions by producing a low level of positive end expiratory pressure (PEEP) that will prevent airways from collapsing.

HFNC is a device that delivers gas through an air/oxygen blender generating flows up to 60 L/min, which is significantly greater than 1-6 L/min flow used with standard nasal cannulas⁵. The enhanced flow delivered via HFNC has several physiological consequences, which can potentially benefit obese patients. One benefit of HFNC is that it can provide PEEP, which is uncommon in open system methods of oxygen delivery⁵. Studies have shown a significant increase in positive pharyngeal pressure and subsequent increases in end expiratory lung volume with the use of HFNC, especially in patients with increased BMI⁶. The added PEEP helps prevent alveolar collapse, enhancing ventilation and oxygen delivery. By increasing the amount oxygen reserve in patients' lungs, the frequency and length of oxygen desaturation caused by the sedation should be decreased; thereby decreasing the requirement of more invasive airway interventions. Another benefit of HFNC is that the high flow rate is able to prevent a build up of CO₂ by washing CO₂ out of the airway dead space⁵. Outcomes that support improvement in oxygenation and ventilation from use of HFNC include a decrease in respiratory

rate and decrease in accessory muscle use during respiration, and increases in the PaO_2 and the $\text{PaO}_2/\text{FiO}_2$ ratio¹⁰.

The actual FiO_2 that low flow systems such as nasal cannulas deliver is usually lower than predicted. As flow rates increase, the actual FiO_2 delivered more closely approaches the predicted value. Using high flow oxygen will, therefore, give an anesthesiologist a better estimate of the concentration of oxygen that is delivered to the patient⁵. The air delivered via HFNC is both humidified and heated to body temperature, thereby decreasing airway irritation and the incidence of bronchoconstriction, which is more common when cold dry air is used⁷.

The numerous benefits of HFNC have made it a valuable tool to assist in ventilation and oxygenation for patients in the intensive care setting. In theory, HFNC, addresses many of the respiratory complications that occur as a consequence of morbid obesity during sedation for medical procedures. We hypothesize that the use of HFNC during gastro endoscopic procedures requiring sedation in extremely obese ($\text{BMI} > 40 \text{ kg/m}^2$) patients will improve ventilation and oxygenation and decrease the need for airway manipulation and increasing FiO_2 levels during the procedure.

OUTCOMES

The primary endpoint is to assess the effects of HFNC on maintaining ventilation and oxygenation. This will be ascertained through the need for airway manipulations such as chin lift and jaw thrust to the placement of airway adjuncts such as oral or nasal airways.

In addition, the need for an increased FiO₂ will be recorded. Secondary endpoints will include the lowest and mean pulse oximetry readings, TcCO₂, TcO₂, and the change in these values from the beginning to the end of the procedure. Additional end points will record interruption or aborting of the procedure secondary to difficulties managing the patient's airway. Both groups will be placed on supplemental oxygen via nasal cannula and transported to the recovery room for observation prior to discharge. Pulse oximetry readings will be followed for an hour every 15 minutes after the completion of the procedure in the recovery room to assess for desaturation. Participants will also be evaluated on how they feel prior to discharge.

MATERIALS AND METHODS:

STUDY POPULATION

Participants are eligible for the study if they are greater than 18 years of age and are scheduled for an elective ambulatory upper and/or lower endoscopy under sedation in the gastrointestinal suite at the Moses Campus of the Montefiore

Medical Center. Participants must have a BMI greater than or equal to 40 kg/m².

Inclusion in the study will be voluntary without monetary compensation.

Participants will be excluded if they are less than 18 years of age, pregnant, have severe respiratory failure (hypercapneic and/or hypoxemic), use home oxygen at baseline, have a tracheostomy, or the procedure is an emergency. Patient selection will be obtained by reviewing the GI suite schedule a few days ahead of time screening for patient with a BMI greater than 40.

The patient's chart will then be reviewed during the normal anesthesia pre-operative assessment for criteria that would exclude the patient from the study. If no exclusion criteria are found, the patient will be contacted by phone and the study will be explained and the patient verbally consented. On the day of the procedure or if possible prior to the procedure the patient will sign written consent. The patients will be consented by a member of the study team.

STUDY DESIGN

Eligible patients will be randomized into two groups of thirty patients each¹¹,
¹². The experimental group will receive oxygen via HFNC at 50 lpm and FiO₂ of 0.35 for the procedure. The control group will receive oxygen via nasal cannula at 5lpm (approximately an FiO₂ of 0.35) for the procedure. Each participant will receive monitored anesthesia care (MAC) with moderate sedation with Propofol.

A loading dose of 1 mcg/kg ideal body weight followed by an infusion starting at 125 mcg/kg/min and titrated to desired level of sedation. At the discretion of the Anesthesiologist the patient may receive 50 to 100mcg of Fentanyl IV PRN. All patients will be monitored using standard American Society of Anesthesiologists monitors, which include continuous EKG, heart rate, pulse oximetry, and non-invasive blood pressure monitoring. Monitoring end tidal carbon dioxide (ETCO₂) to insure adequate ventilation by capnography during moderate sedation can be problematic, due to movement of the cannula or patient preference for mouth breathing preventing adequate uptake of expired gas for analysis. In addition, the high flow rates of the HFNC prevent the measurement of ETCO₂. Ventilation will be monitored in both groups by observing chest movement and by ECG derived respiratory signals¹³. In addition, transcutaneous CO₂ (TcCO₂) and O₂ (TcO₂) levels will be monitored throughout the procedure.

Airway maneuvers required to aid in ventilation or oxygenation during the sedation portion of the procedure will be recorded and are classified as chin lift maneuver, airway insertion, increased FiO₂, active ventilation, and lastly aborting of procedure or intubation. Chin lift maneuver is characterized by lifting of the chin or jaw-thrust maneuver in order to improve ventilation and/or oxygenation. Insertion of an oral or nasal airway helps insure patency of the airway by preventing obstruction by the tongue. Increased FiO₂ will be achieved by

placement of face-mask over the patient's mouth and nose, airway patency can be helped by applying a low level of positive pressure. If oxygenation and/or ventilation continues to be problematic active ventilation can will be performed. The last classification is for any procedure that is aborted early due to respiratory complications or if the patient requires general anesthesia and intubation in order to insure proper ventilation/ oxygenation.

This is a pilot study, so a small number of patients per group was initially chosen. The number of patients in each group is based on our clinical observation while caring for patients in the endoscopy suite. The analysis of the outcome data, the proportion of patients requiring additional airway support, will be analyzed utilizing chi-square analysis. Current clinical practice at our hospital varies, the use of HFNC is a physician preference. Even though it is considered as a standard of care, not all Anesthesiologists are experienced using it. If the Anesthesiologist assigned to the case is not familiar with or not comfortable with HFNC, the patient will be excluded from the study. Although MAC sedation utilizing a nasal cannula for oxygenation is routinely performed, a significant number of morbidly obese patients are electively intubated and placed under general anesthesia for these endoscopic procedures. Patients that are endotracheal intubated will be excluded from the study. The research portion of the study is randomly assigning the

patients into one of two groups, every thing else follows the standard of care at our hospital.

RANDOMIZATION

This is a randomized controlled study. Anesthesia research office that is not part of the patient's routine clinical care will generate the randomization list.

Envelope containing computer generated randomized allocations will be given to the research team. Randomization envelopes will only be open 30 minutes prior to the procedure. To maintain the proper concealed allocation the research team will maintain a randomization sheet with randomization number, subject initials, time and date of the procedure.

As all data is to remain anonymous and to be reported in aggregate (any value less than 1% will be aggregated with the most similar group (including diagnosis and age), we anticipate minimal physical, psychological risks to individual patients.

Data will remain de-identified and no personal identifiers will be queried unless an outlier is found. Subsequent to review by the research team any outliers that cannot be excluded will receive a chart review. For chart review the IRB code will be kept in the desk of and used exclusively by the principle investigator.

Following identification by the principal investigator, charts of outliers may be

reviewed for verification of number of opiate prescriptions. This data will be reconfirmed in the anonymized database/spreadsheet.

STATISTICAL ANALYSIS

Sample size calculation

Primary objective of this study is to evaluate the effects of HFNC on maintaining ventilation and oxygenation in the two groups. For the purpose of this study if a patient is getting 5 or more air way manipulations such as chin lift and jaw thrust or any other direct interventions to maintain the ventilation and oxygenation will be categorized into the group need for additional support to maintain ventilation and oxygenation. According to our clinical audit when using the standard of care nasal cannula 90% of the patients required additional support for maintaining ventilation and oxygenation. HFNC is now been routinely used in our ORs. We have observed that in majority of the patients when HFNC was used the need for additional airway manipulations were minimal when compared to the regular oxygen cannula. For the purpose of this pilot study sample size calculations are based on the assumptions that 90% of patients using regular cannula will require additional airway manipulations while only 55% in the HFNC group requires the same. Based on a two-sided alpha of 0.05 and Type II error of 20% to achieve a statistically

significant difference between the two groups we need to study 25 patients in each group, a total of 50 patients. Additionally, we plan to increase our sample size by 10% to accommodate for attritions.

Analysis plan

All the analysis will be intention-to-treat analysis. Standard descriptive statistics will be used to explain demographic and clinical characteristics (age, gender, type of surgery, pre-entry medications, ASA status, surgeon, co-morbidities, etc.). The analysis plan assumes that the primary outcome of the trial the proportion of patients requiring addition airway support will be analyzed using the chi-square analysis. Percentage of patients requiring FiO₂ will also be analyzed using chi-square analysis. For all continuous monitoring measurements such as TcCO₂ and TcO₂ the measurements will be averaged for first 5 minutes before the start of any procedure activities and this measurement will serve as the baseline measurement. For all subsequent measurements every 15 minute measurements will be averaged and a delta value will be created comparing it to the baseline. The delta value created will be compared between the two groups.

CONCLUSION:

In the past decade, the obesity epidemic has resulted in a growing need for novel approaches to improve patient safety when receiving anesthesia. First shown

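### The primary-outcome rule is not tied to the recorded classes of airway support, so a procedure aborted for respiratory reasons after fewer than five maneuvers can be scored as not needing support

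*Combined protocol and SAP*

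**What the plan says.** All references are to the combined protocol and SAP.

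- **Outcomes.** "Additional end points will record interruption or aborting of the procedure secondary to difficulties managing" the patient's airway. Both interruption and aborting are therefore named, as endpoints separate from the primary one.
- **Study Design.** Five classes of airway support are recorded: chin lift or jaw thrust, airway insertion, increased FiO₂, "active ventilation, and lastly aborting of procedure or intubation". The fifth is then defined: "The last classification is for any procedure that is aborted early due to respiratory complications", or for a patient who needs general anesthesia and intubation. Temporary interruption is in none of the five.
- **Study Design, later.** "Patients that are endotracheal intubated will be excluded from the study".
- **Sample size calculation.** A patient is classed as needing additional support "if a patient is getting 5 or more air way manipulations such as chin lift and jaw thrust or any other direct interventions"; the sentence continues that these serve to maintain ventilation and oxygenation. It names neither aborting nor interruption and does not point back to the five classes.
- **Analysis plan.** All analyses are intention-to-treat. Chi-square tests are planned for need for support and for FiO₂, and between-group comparisons for changes in the continuous monitoring measurements such as TcCO₂ and TcO₂. No comparison of interrupted or aborted procedures is planned.

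**The concern.** The primary outcome is a yes/no classification, and the most severe class of airway support has no stated place in it. Aborting also stops the count: a patient whose procedure ends early has less time to reach five maneuvers. If the threshold governs everything, the worst airway course can be scored as a success.

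Intubation raises a second difficulty. It shares the last class with aborting, yet intubated patients are excluded from the study. If that covers intubation after randomization, the event leaves both numerator and denominator, which conflicts with intention-to-treat.

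The documents describe no blinding, and the two devices are easily told apart. The decision to stop or pause is therefore made by staff who can know the allocation, so an unstated scoring rule should not be left for data handling to settle.

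**Working it through.** **1. The plan's sample size.** Inputs from Sample size calculation: "90% of patients using regular cannula will require additional airway manipulations while only 55% in the HFNC group requires the same", two-sided alpha 0.05, Type II error 20%. With pooled variance, no continuity correction and p̄ = (0.90 + 0.55)/2 = 0.725:

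n = [1.960·√(2·0.725·0.275) + 0.842·√(0.90·0.10 + 0.55·0.45)]² / 0.35² = (1.238 + 0.489)² / 0.1225 = 24.3, so 25 per group.

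The stated 25 reproduces. Power at 25 is 81.1% by this approximation and 83.8% by exact enumeration of the Pearson chi-square. The sample size is not in question.

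**2. The rule under its two readings.** Take, for illustration, a patient who has three chin lifts and is then aborted for respiratory complications.

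| Reading of the rule | Score |
|---|---|
| Any other direct intervention qualifies alone, and aborting is one | Needs support |
| Any other direct intervention qualifies alone, but aborting is not one | 3 < 5: no support needed |
| The threshold of five covers everything | 3 + 1 = 4 < 5: no support needed |

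The text does not choose between these.

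**3. Illustrative size for aborted procedures.** No abort rate is given, so the losses below are assumptions. They take 90% and 55% as the rates with aborts counted, and subtract the points lost when aborts are scored as no support. Power at 25 per group = Φ[(|Δ|√n − 1.960√(2p̄(1−p̄))) / √(p₁(1−p₁) + p₂(1−p₂))]. For control 85% against HFNC 55%: (0.30·5 − 1.960·√0.42)/√0.375 = (1.500 − 1.270)/0.612 = 0.375, and Φ = 64.6%.

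| Points lost, control | Points lost, HFNC | Measured difference | Power |
|---|---|---|---|
| 0 | 0 | 35 | 81.1% |
| 2 | 0 | 33 | 74.9% |
| 5 | 0 | 30 | 64.6% |
| 10 | 0 | 25 | 47.0% |
| 0 | 2 | 37 | 84.8% |
| 0 | 5 | 40 | 89.5% |
| 2 | 2 | 35 | 79.3% |
| 5 | 5 | 35 | 76.9% |

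The higher power in the HFNC-only rows comes from an exaggerated difference.

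**4. Direction for interruptions.** Again no rate is given. Exact chi-square rejection probabilities at 25 per arm, under four assumptions:

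- *Equal share x of below-threshold patients paused.* True rates are 0.90 + 0.10x and 0.55 + 0.45x, so the true difference is 35(1−x): 31.5, 28.0 and 24.5 points at x = 10%, 20% and 30%. A measured 35 points overstates the benefit.
- *Equal share f of true events hidden by pausing.* Measured rates are 0.90(1−f) and 0.55(1−f), so the measured difference is 35(1−f), for example 31.5 points at f = 10%. The benefit is understated. With a true 90% in both arms, rejection is 5.4%, 5.5% and 5.4% at f = 5%, 10% and 20%, against 4.9% with none hidden.
- *Hidden in HFNC only, true 90% in both arms.* Rejection is 8.0%, 15.3% and 38.9% at f = 5%, 10% and 20%.
- *Hidden in control only, true 90% against 55%.* Power falls from 83.8% to 68.9%, 52.8% and 25.8%.

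The sign depends on the assumption, and the documents support none over the others.

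**5. Cost of moving interruptions into the primary outcome.** Under the first assumption in step 4, exact power at 25 per arm is 78.3%, 71.9% and 64.4% at x = 10%, 20% and 30%, against 83.8%. At the thirty per group in Study Design it is 84.1%, 77.9% and 70.8%, against 89.1%.

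**The case against.** The generous reading of the rule is natural. Study Design introduces all five classes as measures required to aid ventilation or oxygenation, and the rule refers to interventions serving the same purpose, so an abort would count alone. Study Design also describes escalating support, so an aborted patient has probably had a mask or active ventilation first. Both points stand as an account of what the authors may have meant. They do not remove the ambiguity, because under the threshold reading those supports also have to add up to five.

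The exclusion of intubated patients follows a sentence about elective intubation and may mean only that. This is plausible but not stated.

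Four stronger conclusions might be inferred, and the documents do not support them:

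- *That aborting is missing from the recorded support.* It is listed and defined; only temporary interruption is absent.
- *That an aborted patient is certainly misscored.* This follows on some readings only.
- *That the gap inflates the HFNC benefit, even with equal use of pausing.* That depends on what is held equal; the opposite result is as easily obtained.
- *That interruption must be part of the primary outcome.* Outcomes keeps it as a separate endpoint, which is a legitimate choice, and merging it costs power.

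**Conclusion.** The point holds as a defect in the definition of the primary outcome. The rule does not say which of the five classes count alone and which need the count of five, so a procedure aborted for respiratory complications after fewer than five maneuvers can be scored as not needing support. Interruption is named as an endpoint but has neither a recording class nor a planned comparison.

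The size cannot be estimated, because no abort or interruption rate is given. Under the assumed losses in step 3, power at 25 per group ranges from 47.0% to 89.5%, around a reproduced 81.1%. The direction of bias is not established. The stated 25 per group is unaffected.

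**What to change.** 1. Under Sample size calculation, state that a patient in the last Study Design class (procedure aborted for respiratory reasons, or intubated during sedation) counts as needing additional support whatever the number of maneuvers. For each of the other four classes, say whether it counts alone or only towards the five.
2. Reconcile this with the exclusion of intubated patients and with intention-to-treat: say whether the exclusion means elective intubation before randomization only, and how a patient intubated afterwards is analyzed.
3. Keep interruption as the separate endpoint in Outcomes. Give it a place in data recording and compare interrupted and aborted procedures by arm in the Analysis plan.
4. Add a sensitivity analysis of the primary outcome that counts airway-related interruptions as events.

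The cost is wording: the last class is already recorded and Outcomes already calls for interruptions to be recorded. The control rate may move slightly nearer its ceiling; the documents give no rate from which to size this. It should also be checked whether the audit behind the 90% figure counted aborted procedures. Using interruption only in a sensitivity analysis avoids the power loss in step 5 for the primary test.

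### The primary outcome is a discretionary act by a clinician who can see the device, and the gas-exchange measurements are not tied to the conclusion drawn from it

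*Combined protocol and SAP*

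**What the plan says.** - **Aim and primary endpoint (Outcomes).** The aim is physiological, to maintain ventilation and oxygenation. The measure is behavioral: "This will be ascertained through the need for airway manipulations such as chin lift and jaw thrust" and the placement of airway adjuncts.
- **Event definition (Statistical Analysis, Sample size calculation).** A patient counts as needing additional support after five or more manipulations, or other direct interventions. The proportion is compared by chi-square.
- **Maneuver definition (Study Design).** "Chin lift maneuver is characterized by lifting of the chin or jaw-thrust maneuver in order to improve ventilation and/or oxygenation". No SpO2, TcCO2 or apnea criterion says when a maneuver is called for. Maneuvers are recorded, but the recorder is not named.
- **Awareness of treatment (Study Design; Randomization).** One arm has HFNC at 50 lpm and the other a nasal cannula at 5 lpm. Envelopes are opened 30 minutes before the procedure. No masking of operator, recorder or assessor is described. A patient whose anesthesiologist is not comfortable with HFNC is excluded.
- **Prior expectation (Sample size calculation).** "We have observed that in majority of the patients when HFNC was used the need for additional airway manipulations were minimal" compared with the regular cannula.
- **Objective measures (Outcomes; Analysis plan).** "Secondary endpoints will include the lowest and mean pulse oximetry readings", together with TcCO2, TcO2 and their changes. For the continuous measures the Analysis plan defines a 5-minute baseline, 15-minute averages and a between-group comparison of changes. It names no test for these and states no link to the primary conclusion.

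**The concern.** The recorded count depends on two things: how well the patient breathes, and how readily the clinician acts. The device may improve the first. Knowing which device is in use may change the second. The chi-square test sees only the count and cannot separate them.

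If staff wait longer before lifting the chin because they trust HFNC, the HFNC arm will show fewer events with no change in gas exchange. Under the plan, that result could be reported as HFNC maintaining ventilation and oxygenation with less support. SpO2 and TcCO2 from the same patients would bear on which explanation is right, but the plan gives them no role in the conclusion.

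**Working it through.** **1. The plan's own figure.** Inputs from the Sample size calculation are two-sided alpha 0.05, 80% power, and 90% versus 55%. With pooled variance and no continuity correction, the average rate is (0.90 + 0.55)/2 = 0.725, and

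n = [1.960·√(2 × 0.725 × 0.275) + 0.842·√(0.90 × 0.10 + 0.55 × 0.45)]² / 0.35² = 24.3, rounded up to 25 per group.

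This matches the plan ("significant difference between the two groups we need to study 25 patients in each group, a total of 50 patients"). The sample size is correct for its inputs; the issue is how the outcome is ascertained. Adding 10% gives 25 × 1.1 = 27.5, or 28 per group, and Study Design plans 30. The checks below use 25 and 30.

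**2. How many patients must change category.** Take 30 per arm with control at its assumed 90%, that is 27/30.

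- HFNC 21/30: p = 0.053, not significant.
- HFNC 20/30: pooled rate 47/60 = 0.783, standard error √(0.783 × 0.217 × 2/30) = 0.106, z = 0.233/0.106 = 2.19, p = 0.028.

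Seven HFNC patients falling below the definition are therefore enough. With Yates' correction or Fisher's exact test it takes eight (19/30). The plan does not say which form of chi-square is meant.

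**3. Shift in willingness to act.** Assumptions, none of them given in the documents:

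- there is no true device effect, and 90% are positive in control;
- only the five-or-more route is affected;
- counts are Poisson, or negative binomial with variance m + m²/k.

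The mean m is set so that P(5 or more) = 0.90. This gives m = 7.99 (Poisson), 11.6 (k = 5) and 19.6 (k = 2). The HFNC mean is then cut by 20% or 30%. The chance of p < 0.05 (two-sided Pearson) comes from enumerating both binomials at 25 and 30 per arm.

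| Count model | Cut | Recorded HFNC rate | Chance of significance, 25 to 30 per arm |
|---|---|---|---|
| Poisson | 20% | 76% | 26-29% |
| Poisson | 30% | 66% | 58-64% |
| Neg. binomial, k = 5 | 20% | 83% | 12-13% |
| Neg. binomial, k = 5 | 30% | 77% | 24-27% |
| Neg. binomial, k = 2 | 20% | 86% | about 8% |
| Neg. binomial, k = 2 | 30% | 83% | 12-13% |

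The nominal figure is 5%. In these rows nearly all significant results favor HFNC. With a 10% cut the chance is 9-10% under Poisson and about 6% with k = 2, which is close to nominal.

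**4. If some patients qualify by another route.** Suppose 30% or 50% of patients are positive through other direct interventions that do not shift. Under Poisson, the 20% cut then gives 20-22% or 15-17% instead of 26-29%.

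**The case against.** **The objective data are already planned.** This stands. Lowest and mean SpO2, TcCO2, TcO2 and their changes are prespecified and compared by arm. A reader might infer that the trial has no objective check, or that a threshold effect could never be detected. The documents do not support that. The gap is narrower: no rule connects these results to the primary conclusion, and nothing records the patient's state when a maneuver begins.

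**The Poisson figures are the strongest case.** This also stands. Poisson gives every patient the same underlying rate. The trial mixes upper and lower endoscopy, titrated propofol and optional fentanyl, so variation between patients is likely and the lower rows of the table may be nearer the truth. A continuity correction lowers the figures further: at 30 per arm and a recorded HFNC rate of 75%, from 34% to 21%.

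**A large shift is needed for a typical significant result.** Seven of 30 patients is 23 points, two thirds of the planned 35. A reader might infer that a modest change in habits would produce significance. The figures show that it could under some assumptions, not that it would.

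**Lack of blinding is inferred.** The documents do not call the trial open-label or name the recorder, and the stated expectation is the protocol team's, not necessarily that of each treating anesthesiologist. Still, a 50 lpm and a 5 lpm system cannot look alike to the person managing the airway.

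**It is a pilot.** That tempers the urgency. The plan nonetheless sets alpha and power for a significance test, and its Conclusion section hypothesizes improved and safer ventilation.

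**Conclusion.** The concern holds in limited form. The primary event is a discretionary act without a stated trigger, taken by someone who can see the device, and the objective secondary results have no stated part in interpreting it. The plan as written could therefore turn a difference in willingness to act into a claim about ventilation and oxygenation.

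The size is uncertain. Across the three count models, the chance of a false significant result is about 8-29% for 20% fewer maneuvers and 12-64% for 30% fewer, on the assumptions set out in the working. These are illustrations, not predictions. Nothing in the documents shows that staff will act differently by arm. Bias could also run against HFNC, although the stated expectation and the restriction to operators comfortable with HFNC make bias in its favor the main worry. This is a worthwhile, inexpensive improvement rather than a fatal flaw.

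**What to change.** 1. On the existing maneuver record, enter the time and the SpO2 and TcCO2 displayed when each maneuver starts. Compare these values between arms to show whether the threshold for acting differed.
2. Name lowest SpO2 and change in TcCO2 as key supporting outcomes. Report them beside the primary result as between-group differences with 95% confidence intervals, with total propofol and fentanyl by arm. Both measures are needed. The Background says that low-flow cannulas usually deliver less oxygen than predicted, so SpO2 alone could favor HFNC without better ventilation. Study Design says that end-tidal CO2 cannot be measured on HFNC.
3. State in the SAP that a significant primary result alone supports only fewer maneuvers recorded in an unblinded comparison. Wording that HFNC maintains ventilation and oxygenation with less support must rest on those intervals, judged against a margin that the sponsor sets in advance, or be presented as descriptive. A bare requirement that neither measure be worse would not work without a margin.

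A sensitivity analysis restricted to maneuvers accompanied by a monitor change is not recommended. It filters maneuvers that were performed and cannot recover those that were withheld, which is the bias at issue.

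**Cost.** Two reading columns and a time entry on an existing form, SAP text, a little more analysis, and possibly a less favorable permitted conclusion. No extra observer and no change to care.
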